## 14. APPENDICES

### 14.1 APPENDIX 1 – LIST OF PROHIBITED CONCOMITANT MEDICATIONS

alfentanil	mexiletine
almotriptan	naratriptan
alprenolol	nefazodone
amitriptyline	nortriptyline
amphetamine	ondansetron
astemizole	oxcarbazepine
atomoxetine	oxycodone
bufuralol	paroxetine
bupropion	perphenazine
bupirone	phenacetin
cafergot	phenobarbital
cannabidiol	phenytoin
carbamazepine	promethazine
cerivastatin	propafenone
citalopram	retigabine/ezogabine
clomipramine	risperidone
codeine	ritonavir
cyproheptadine	rizatriptan
desipramine	selegiline
dextromethorphan	sertraline
duloxetine	sumatriptan
eletriptan	telaprevir
encainide	the and derivatives
ergotamine tartrate	tramadol
eslicarbazepine	trazodone
felbamate	vortioxetine
fentanyl	zolmitriptan
fluoxetine	zuclopenthixol
fluvoxamine	
frovatriptan	
imipramine	
levacetylmethadol (laam)	
linezolid	
meperidine	
methadone	
metoclopramide	

14.2 APPENDIX 2 – COLUMBIA – SUICIDE SEVERITY RATING SCALE

**COLUMBIA-SUICIDE SEVERITY  
RATING SCALE  
(C-SSRS)**

Children's Baseline/Screening

Version 6/23/10

*Posner, K.; Brent, D.; Lucas, C.; Gould, M.; Stanley, B.; Brown, G.; Fisher, P.; Zelazny, J.;  
Burke, A.; Oquendo, M.; Mann, J.*

[figure not shown]
**Disclaimer:**

*This scale is intended to be used by individuals who have received training in its administration. The questions contained in the Columbia-Suicide Severity Rating Scale are suggested probes. Ultimately, the determination of the presence of suicidal ideation or behavior depends on the judgment of the individual administering the scale.*

*Definitions of behavioral suicidal events in this scale are based on those used in **The Columbia Suicide History Form**, developed by [name] and [name], Conte Center for the Neuroscience of Mental Disorders (CCNMD), New York State Psychiatric Institute, [name]. (Oquendo M. A., Halberstam B. & Mann J. J., Risk factors for suicidal behavior: utility and limitations of research instruments. In M.B. First [Ed.] Standardized Evaluation in Clinical Practice, pp. 103-130, 2003.)*

[figure not shown]
*For reprints of the C-SSRS contact [name]., New York State Psychiatric Institute, [name]; inquiries and training requirements contact [[contact]](mailto:[contact])*

© 2008 The Research Foundation for Mental Hygiene, Inc.

This document  
applicatio

orization  
st.

This document is confidential and its disclosure is prohibited without the prior written authorization of Zogenix International Limited.

# COLUMBIA-SUICIDE SEVERITY RATING SCALE (C-SSRS)

Children's Since Last Visit

Version 6/23/10

*Posner, K.; Brent, D.; Lucas, C.; Gould, M.; Stanley, B.; Brown, G.; Fisher, P.; Zelazny, J.;  
Burke, A.; Oquendo, M.; Mann, J.*

[figure not shown]
#### Disclaimer

This scale is intended to be used by individuals who have received training in its administration. The questions contained in the Columbia-Suicide Severity Rating Scale are suggested probes. Ultimately, the determination of the presence of suicidal ideation or behavior depends on the judgment of the individual administering the scale.

Definitions of behavioral suicidal events in this scale are based on those used in **The Columbia Suicide History Form**, developed by [name] and [name], Conte Center for the Neuroscience of Mental Disorders (CCNMD), New York State Psychiatric Institute, [name]. (Oquendo M. A., Halberstam B. & Mann J. J., Risk factors for suicidal behavior: utility and limitations of research instruments. In M.B. First [Ed.] Standardized Evaluation in Clinical Practice, pp. 103-130, 2003.)

[figure not shown]
For reprints of the C-SSRS contact [name]., New York State Psychiatric Institute, [name]; inquiries and training requirements contact [[contact]](mailto:[contact])

© 2008 The Research Foundation for Mental Hygiene, Inc.

This document contains confidential information and is intended for use only in the application.

[figure not shown]
Confidential Information  
Authorization

This document is the property of Zogenix International Limited. All rights reserved. No part of this document may be reproduced, stored in a retrieval system, or transmitted in any form or by any means, electronic, mechanical, photocopying, recording, or by any information storage and retrieval system, without the prior written permission of Zogenix International Limited.

[figure not shown]
Authorization  
of.

**14.3 APPENDIX 3 – BEHAVIOR RATING INVENTORY OF EXECUTIVE  
FUNCTION – PRESCHOOL VERSION**

[figure not shown]

authorization  
hereof.

[figure not shown]

[figure not shown]

[figure not shown]
[figure not shown]
This document is confidential and its disclosure is prohibited without the prior written approval of Zogenix International Limited.

This document is the property of Zogenix International Limited. All rights reserved. No part of this document may be reproduced, stored in a retrieval system, or transmitted in any form or by any means, electronic, mechanical, photocopying, recording, or by any information storage and retrieval system, without the prior written permission of Zogenix International Limited.

[figure not shown]

[figure not shown]
This document

[figure not shown]
ization

[figure not shown]
This doc

ation

[figure not shown]

[figure not shown]

14.4 APPENDIX 4 – QUALITY OF LIFE IN CHILDHOOD EPILEPSY SCALE

[figure not shown]

This document cannot be used for any application and any extension thereof. without the prior written authorization of Zogenix International Limited.

[figure not shown]
Authorization  
hereof.

This document  
applies

[figure not shown]
This document cannot be used to support any application and any extensions or variations of the original application. This document is for informational purposes only. It is not intended to be used for regulatory submission.

PUBLIC COPY

[figure not shown]

This document is  
applicable

Authorization  
proof.

[figure not shown]

**14.5 APPENDIX 5 – TANNER STAGING**

[figure not shown]

[figure not shown]
This document is confidential and its disclosure is prohibited without the prior written consent of Zogenix International Limited.

[figure not shown]
ization

[figure not shown]

[figure not shown]
**14.6 APPENDIX 6 – PEDSQL**

[figure not shown]

[figure not shown]

[figure not shown]

[figure not shown]

[figure not shown]

[figure not shown]

[figure not shown]

[figure not shown]

[figure not shown]

14.7 APPENDIX 7 – EQ-5D-5L QUESTIONNAIRE

[figure not shown]

**14.8 APPENDIX 8 – HOSPITAL ANXIETY AND DEPRESSION SCALE**

This document cannot be used to support any marketing authorization and any extensions or variations thereof.

14.9 APPENDIX 9 – MAXIMUM ALLOWABLE BLOOD DRAW VOLUMES

Maximum allowable blood draw volumes:

PATIENT'S WEIGHT		TOTAL VOLUME	MAXIMUM mL IN ONE BLOOD DRAW	MAXIMUM mL IN A 30-DAY PERIOD
Kg	lbs	mL	2.5% of total blood vol	5% of total blood vol
1	2.2	100	2.5	5
2	4.4	200	5	10
3	6.6	240	6	12
4	8.8	320	8	16
5	11	400	10	20
6	13.2	480	12	24
7	15.4	560	14	28
8	17.6	640	16	32
9	19.8	720	18	36
10	22	800	20	40
11 thru 15	24 thru 33	880-1200	22-30	44-60
16 thru 20	35 thru 44	1280-1600	32-40	64-80
21 thru 25	46 thru 55	1680-2000	42-50	84-100
26 thru 30	57 thru 66	2080-2400	52-60	104-120
31 thru 35	68 thru 77	2480-2800	62-70	124-140
36 thru 40	79 thru 88	2880-3200	72-80	144-160
41 thru 45	90 thru 99	3280-3600	82-90	164-180
46 thru 50	101 thru 110	3680-4000	92-100	184-200
51 thru 55	112 thru 121	4080-4400	102-110	204-220
56 thru 60	123 thru 132	4480-4800	112-120	224-240
61 thru 65	134 thru 143	4880-5200	122-130	244-260
66 thru 70	145 thru 154	5280-5600	132-140	264-280
71 thru 75	156 thru 165	5680-6000	142-150	284-300
76 thru 80	167 thru 176	6080-6400	152-160	304-360
81 thru 85	178 thru 187	6480-6800	162-170	324-340
86 thru 90	189 thru 198	6880-7200	172-180	344-360
91 thru 95	200 thru 209	7280-7600	182-190	364-380
96 thru 100	211 thru 220	7680-8000	192-200	384-400

Based on blood volume of:

- 1 to 2 kg      100 mL/kg      (pre-term infant)
- >2 kg      80 mL/kg      (term infant - adult)

This information is similar to that used by the Committee on Clinical Investigations at Children's Hospital in Los Angeles, and at Baylor College of Medicine in Dallas, TX.

Adapted by [redacted] August 2001  
 Children's Hospital and Regional Medical Center Laboratory  
 Seattle, WA

Maximum allowable blood draw volumes:

[figure not shown]
PATIENT'S WEIGHT		TOTAL VOLUME	MAXIMUM mL IN ONE BLOOD DRAW	MAXIMUM mL IN A 30-DAY PERIOD
Kg	lbs	mL	2.5% of total blood vol	5% of total blood vol
1	2.2	100	2.5	5
2	4.4	200	5	10
3	6.6	240	6	12
4	8.8	320	8	16
5	11	400	10	20
6	13.2	480	12	24
7	15.4	560	14	28
8	17.6	640	16	32
9	19.8	720	18	36
10	22	800	20	40
11 thru 15	24 thru 33	880-1200	22-30	44-60
16 thru 20	35 thru 44	1280-1600	32-40	64-80
21 thru 25	46 thru 55	1680-2000	42-50	84-100
26 thru 30	57 thru 66	2080-2400	52-60	104-120
31 thru 35	68 thru 77	2480-2800	62-70	124-140
36 thru 40	79 thru 88	2880-3200	72-80	144-160
41 thru 45	90 thru 99	3280-3600	82-90	164-180
46 thru 50	101 thru 110	3680-4000	92-100	184-200
51 thru 55	112 thru 121	4080-4400	102-110	204-220
56 thru 60	123 thru 132	4480-4800	112-120	224-240
61 thru 65	134 thru 143	4880-5200	122-130	244-260
66 thru 70	145 thru 154	5280-5600	132-140	264-280
71 thru 75	156 thru 165	5680-6000	142-150	284-300
76 thru 80	167 thru 176	6080-6400	152-160	304-360
81 thru 85	178 thru 187	6480-6800	162-170	324-340
86 thru 90	189 thru 198	6880-7200	172-180	344-360
91 thru 95	200 thru 209	7280-7600	182-190	364-380
96 thru 100	211 thru 220	7680-8000	192-200	384-400

Based on blood volume of:  
 1 to 2 kg 100 mL/kg (pre-term infant)  
 >2 kg 80 mL/kg (term infant - adult)  
 This information is similar to that used by the Committee on Clinical Investigations at Children's Hospital in Los Angeles, and at Baylor College of Medicine in Dallas, TX.

Adapted by [redacted] August 2001  
 Children's Hospital and Regional Medical Center Laboratory  
 Seattle, WA

**14.10 APPENDIX 10 – KAROLINSKA SLEEPINESS SCALE**

This document cannot be used to support  
application and any extensions or va  
PUBLIC CO

## 14.11 APPENDIX 11 - STUDY CONDUCT DURING COVID-19

In March 2020, the World Health Organization declared a global pandemic related to an illness caused by a novel coronavirus known as COVID-19. As a result, public health initiatives, such as laws, regulations and policies were enacted at country and institutional levels to protect the health of the general public. These initiatives and policies have affected the ability of study sites to conduct the trial per protocol and the ability of the sponsor and/or delegate to conduct trial oversight and monitoring visits.

In an effort to support the rights, safety and welfare of subjects and ensure as little impact on the integrity of the research as possible the following alternative processes have been implemented due to restrictions related to COVID-19. Though every attempt should be made to conduct study visits per protocol, any implementation of alternative processes should be properly documented.

### 1. Allowance of Delays to In-person Study Visits

If sites are unable to conduct study visits, or subjects are unable to travel to the study site due to COVID-19 circumstances, an in-person visit may be delayed up to 6 weeks from the protocol-defined visit due date. Data will need to be entered per normal procedures in the EDC, with a description indicating COVID-19 as the cause for delay in response to queries. If a subject is unable to travel to the study site within this expanded 6-week window, a telephone or video telemedicine visit should be attempted, as described below. If a telephone or video telemedicine visit cannot be conducted in the 6-week window, the visit should be considered missed and the next scheduled visit conducted.

### 2. Allowance of Remote Telemedicine/Telephone/Video Visits:

Visit 1 should be conducted in person. For Visits 2 through 15, remote visits via telephone or video are acceptable when subjects are unable to travel to the site for in-person visits due to COVID-19 circumstances. The following information should be collected and recorded in the source documentation and in the EDC where applicable. Log pages (e.g. AEs, concomitant medication changes) will be entered normally as they are not associated with specific visits; assessment forms located within a particular visit page will also be entered normally, however, queries will be fired to capture specific information explaining the basis for missing or alternatively collected (ie. remote) data. Detailed instruction for EDC entry may be found in the CRF Completion Guidelines (CCGs).

- Date and time of the telephone/video visit
- Any changes in health status
- AEs/SAE assessment
- Concomitant medication query
- Review seizure and medication diary with parent/caregiver for compliance and any abnormalities in seizure activity
- Scales and Questionnaires, when applicable and if feasible
  - C-SSRS
  - CGI-I (by Investigator)

- Tanner Staging

### **3. End-of-Study/Early Termination (EOS/ET) and Follow-up Visits:**

Cardiac follow-up visits must be conducted in-person.

EOS/ET for subjects tapering off ZX008:

For the EOS/ET visit (Visit 16) and Post-Dosing Follow-up visit (Visits 17-19), every attempt should be made to conduct these visits in-person. For subjects tapering off study-drug that are unable to come to the study site, the EOS/ET and Post-Dosing Follow-up visits may be conducted via telephone or video. However, subjects should return to the study site in person, as soon as feasible to conduct any safety assessments that were unable to be evaluated remotely. If an in-person visit cannot be scheduled within 6 months of the EOS/ET and/or Post-Dosing Follow-up visit windows, these visits will be considered as missed.

EOS/ET for subjects transitioning to Commercial drug:

For the EOS/ET visit (Visit 16) and Post-Dosing Follow-up visit (Visit 17), every attempt should be made to conduct these visits in-person. For subjects tapering off study-drug that are unable to come to the study site, the EOS/ET and Post-Dosing Follow-up visits may be conducted via telephone or video. However, subjects should return to the study site in person, as soon as feasible to conduct any safety assessments that were unable to be evaluated remotely. Subjects who transition to commercially available drug must have an ECHO within 3-6 months before starting commercial drug and will have follow-up ECHOs within the required timeframe while on commercial drug.

EOS/ET for subjects transitioning to another extension study:

For subjects transitioning into another ZX008 extension study that are unable to attend the EOS/ET visit due to restrictions to traveling to the study site, delays in the start-up of the extension study, or other COVID-related delays, the EOS/ET visit may be delayed until an in-person visit is conducted. Therefore, subjects may remain on study for longer than the planned duration of participation. If the delay is over 6 weeks, medical monitor review and approval is required. If approval to extend beyond 6 weeks is granted, telephone or video visits should be conducted at least every 12 weeks until the in-person EOS/ET transitional visit to the other extension study is performed. The telephone or video visits will collect the following data, at minimum:

- Date and time of the telephone/video visit
- Any changes in health status
- AEs/SAE assessment
- Concomitant medication query
- Review seizure and medication diary with parent/caregiver for compliance and any abnormalities in seizure activity

4. **Allowance of delays to ECHO, ECG, Chest X-Ray, EEG and clinical lab assessments when in-person study visits are missed or delayed**

If it is not possible to obtain the assessments as described below, a documented risk/benefit discussion with the medical monitor is required to determine a course of action, which may include approval to delay further for a pre-specified duration, subject withdrawal, or other actions. The risk/benefit analysis will take into account report of drug effectiveness, AEs, previous assessment findings, duration of delay, clinical improvement while on study drug (seizure and non-seizure outcomes), and region-specific risk of attending in-person visits to complete the assessments.

Doppler ECHO:

If subjects are unable to travel to the study site due to COVID-19 circumstances, ECHOs may be delayed up to an additional 3 months from the protocol-designated ECHO due date (for a total of 6 months from the time of the last ECHO) for subjects that exhibited the following on their previous, most recent ECHO: absent aortic regurgitation, absent or trace mitral regurgitation, and PASP <30 mmHg.

All subjects with regurgitation  $\geq$  trace aortic regurgitation,  $\geq$  mild mitral regurgitation, or PASP  $\geq$ 30 mmHg may have ECHO delayed from the protocol-designated ECHO due date by up to 6 weeks only. In those cases where an ECHO cannot be performed in the specified time period at the study-authorized facility by a certified sonographer, the Sponsor may approve administration of the ECHO at an alternative facility to minimize subject's need for travel. If the ECHO cannot be performed, a risk/benefit analysis must be conducted as described above.

If a delayed ECHO was conducted within 30 days of a scheduled Cardiac Follow-up Visit, this assessment does not need to be repeated at the Cardiac Follow-up Visit provided there were no findings meeting Level 2 criteria (see Protocol Table 12) that require additional follow-up.

ECG, Chest X-ray and EEG:

If clinically indicated and where applicable, delays in these assessments may be implemented based on the investigators' clinical discretion, weighing the risk/benefit of the clinical necessity of the assessment versus the risk of an in-person visit. All decisions should be documented appropriately in the source documentation. If not conducted at the study site, ECG, chest X-ray and EEG can be performed at any qualified local facility. If not conducted at the study site, results should be sent to the Principal Investigator for safety overread and documentation. If Level 2 or greater findings were observed, then the Cardiac Follow-up Visit should be re-scheduled from the date of the delayed ECHO.

If the ECG (or in the case of certain country-specific regulations: Chest X-ray or EEG) was conducted within 30 days of a scheduled Cardiac Follow-up Visit, these assessments do not need to

be repeated at the Cardiac Follow-up Visit provided there were no significant findings that require additional follow-up.

Clinical Laboratory Assessments:

If clinically indicated and where applicable, delays in these assessments may be implemented based on the investigators' clinical discretion, weighing the risk/benefit of the clinical necessity of the assessment versus the risk of an in-person visit. All decisions should be documented appropriately in the source documentation. If not conducted at the study site, clinical laboratory assessments can be performed at any qualified local facility with results sent to the Principal Investigator for safety overread and documentation.

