#### **4.4 REMOVAL OF SUBJECTS FROM THERAPY OR ASSESSMENT**

While subjects are encouraged to complete all study evaluations, subjects may voluntarily withdraw from the study for any reason at any time. They may be considered withdrawn if they fail to return for visits, or become lost to follow-up for any other reason.

If premature withdrawal occurs for any reason, the investigator must make a genuine effort to determine the primary reason for a subject's premature withdrawal from the study and record this information on the CRF. All subjects who withdraw from the study with an ongoing AE must be followed until the event is resolved or deemed stable. If a subject withdraws prematurely after dosing, all data to be collected prior to discharge from the clinical site should be collected at the time of premature discontinuation or at the scheduled discharge.

For subjects who are lost to follow-up (ie, those subjects whose status is unclear because they failed to appear for study visits without stating an intention to withdraw), the investigator should show "due diligence" by documenting in the source documents the steps taken to contact the subject (eg, dates of telephone calls, registered letters).

Subjects must be discontinued from the study for the following reasons, if deemed appropriate by the Sponsor or investigator:

1. Development of signs or symptoms indicative of cardiac valvulopathy or regurgitation (mitral, aortic, tricuspid, pulmonary valves), or pulmonary hypertension for which IDSMC, in consultation with the IPCAB, the central cardiac reader, and the investigator believe the benefit of continued participation does not outweigh the risk.
2. Subject is found to have entered the clinical investigation in violation of the protocol.
3. Subject requires or starts using the use of an unacceptable or contraindicated concomitant medication.
4. Subject's condition changes after entering the clinical investigation so that the subject no longer meets the inclusion criteria or develops any of the exclusion criteria.
5. Subject is noncompliant with procedures set forth in the protocol in an ongoing or repeated manner.
6. Subject experiences an AE that warrants withdrawal from the clinical investigation.

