### 8.9.1 Follow-up of Echocardiogram Findings

All ECHOs will be evaluated by a central reader from BioMedical Systems, Inc. (BMS), in consultation with the IPCAB, if warranted. Findings related to pulmonary hypertension or valvulopathy on any of the four valves (aortic, mitral, pulmonary, tricuspid) will be reported to the investigator with grades of normal, trace, mild, moderate, or severe. If the ECHO result has progressed in severity since the last reading, then new oversight measures will be enacted as described below in Levels 1-3. Table 12 describes the severity of ECHO findings with the level of increasing oversight if the subject is to remain in the study.

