**Table 12. Clinical Measures Enacted Upon Increasing Severity of ECHO Findings**

Severity	Valve			
	Aortic	Mitral	Pulmonary	Tricuspid
Trace	Level 1	Level 1	Level 1	Level 1
Mild (≤18 years)	Level 2	Level 1	Level 1	Level 1
Mild (>18 years)	Level 2	Level 1	Level 1	Level 1
Moderate	Level 3	Level 2	Level 2	Level 2
Severe	Level 3	Level 3	Level 3	Level 3

Level 1: Continue per protocol

Level 2:

1. If there is a desire to continue study medication:
  - a. The investigator will evaluate the efficacy to date based on study diaries and consult with the parent/guardian, and determine whether study treatment was associated with significant, meaningful benefit in number, severity and/or duration of seizures and/or on the impact on daily functioning.
  - b. The investigator will consider whether the subject has had reasonable trials (dose and duration) of other available anticonvulsants (eg, VPA, CLB, or topiramate), alone or in combination, and not maintained the level of seizure control achieved with study medication.
2. If the investigator feels consideration of continued treatment is warranted considering benefit and potential risk, and the parent/guardian feels strongly that the subject be maintained on the study medication when understanding the risks, the parent/guardian must sign a new consent which describes the additional risk and the subject should provide assent if appropriate.
  - a. If both of these conditions are not met, the subject is discontinued from treatment.

3. The investigator prepares a case history and rationale for continuation to be submitted to the IDSMC for review, including consideration of effects on seizures and comorbidities.
4. The Co-Chairs of the IPCAB are alerted to the request and prepare, after consultation with BMS, an evaluation of the cardiopulmonary risk and proposed monitoring plan if applicable, for submission to the IDSMC.
5. IDSMC will review the submission from the Investigator and the IPCAB and unblind the subject's core study treatment, if warranted.
6. IDSMC makes a determination of appropriate path, including the possible outcomes:
  - a. Discontinue study medication
  - b. Increase frequency of ECHO and ECG monitoring
  - c. Add additional ECG and/or ECHO measures to be monitored
  - d. Reduce the dose of study medication

Level 3:

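### The COVID ECHO-delay rule in Appendix 11, item 4 leaves out the tricuspid and pulmonary valves, so a Level 2 or 3 subject kept on drug can qualify for a longer delay than a Level 1 subject

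*Protocol*

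**What the plan says.** Appendix 11, item 4 (Doppler ECHO) sets two delay classes for subjects who cannot travel because of COVID-19. In the first, "ECHOs may be delayed up to an additional 3 months from the protocol-designated ECHO due date", with a parenthesis putting the total at 6 months since the last ECHO. It is open to subjects whose most recent ECHO showed "absent aortic regurgitation, absent or trace mitral regurgitation, and PASP <30 mmHg". The second class is limited to 6 weeks and covers aortic regurgitation of trace or more, mitral regurgitation of mild or more, or PASP of 30 mmHg or more.

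Elsewhere the protocol looks at four valves. Under Section 8.9.1, findings on "any of the four valves (aortic, mitral, pulmonary, tricuspid) will be reported to the investigator with grades of normal, trace, mild, moderate, or severe". Discontinuation reason 1 in Section 4.4 refers to "cardiac valvulopathy or regurgitation (mitral, aortic, tricuspid, pulmonary valves), or pulmonary hypertension". Table 12, "Clinical Measures Enacted Upon Increasing Severity of ECHO Findings", puts moderate pulmonary or tricuspid regurgitation at Level 2 and severe at Level 3. It puts trace aortic and mild mitral regurgitation at Level 1, which means no change to the protocol schedule.

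Item 4 already uses the Table 12 levels for another purpose. A delayed ECHO can stand in for the one at the Cardiac Follow-up Visit "provided there were no findings meeting Level 2 criteria (see Protocol Table 12) that require additional follow-up", and "If Level 2 or greater findings were observed, then the Cardiac Follow-up Visit should be re-scheduled from the date of the delayed ECHO".

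**The concern.** The delay rule and Table 12 rank the same findings differently. A finding that Table 12 sends to individual review can fall in the lenient delay class, while one that Table 12 lets continue unchanged falls in the strict class. Heart valve disease and pulmonary hypertension are the reasons Section 1.2 gives for fenfluramine's withdrawal from the US market, long-term safety is the primary objective, and ECHO is how the study looks for these conditions. A rule on how long an ECHO may be postponed should not be looser for a subject under closer oversight. No reason for omitting the two valves is stated, and the same item shows that the Table 12 levels were at hand when it was written.

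**Working it through.** **Step 1: are the two classes complete?** The 3-month class needs three conditions together: aortic absent, mitral absent or trace, and PASP below 30 mmHg. The 6-week class applies if any one of them fails. Every subject therefore falls in exactly one class, and tricuspid and pulmonary grades never affect which.

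**Step 2: set the classes against Table 12.**

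| Most recent ECHO (otherwise normal, PASP <30 mmHg) | Table 12 level | Permitted delay |
|---|---|---|
| Trace aortic | 1 | 6 weeks |
| Mild mitral | 1 | 6 weeks |
| Moderate tricuspid or pulmonary | 2 | 3 months |
| Severe tricuspid or pulmonary | 3 | 3 months |

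As a check on how far this reaches, count grade combinations with five grades (absent to severe) per valve. The 3-month class holds 1 (aortic) × 2 (mitral) × 5 (pulmonary) × 5 (tricuspid) = 50. Those with both omitted valves at mild or less number 2 × 3 × 3 = 18. The other 50 − 18 = 32 are Level 2 or 3. These are possible grade patterns, not patients, and say nothing about frequency.

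**Step 3: size in days.** Inputs:
- Routine ECHO interval: the ECHO study days in Tables 1 and 2 (30, 90, 180, 270, 365, then every 90 days to 1085) give 12 intervals, ten of them 90 days.
- Longer delay: 3 months, taken as 90 days. This agrees with the item's own 6-month total, since 90 + 90 = 180.
- Shorter delay: 6 weeks = 42 days.

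Longest nominal gap between ECHOs = interval + permitted delay:
- Level 2 or 3 tricuspid or pulmonary finding, routine interval unchanged: 90 + 90 = 180 days.
- Level 1 trace aortic or mild mitral finding: 90 + 42 = 132 days.
- Excess: 180 − 132 = 48 days.

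If 3 months is 91 or 92 days, the excess is 49 or 50. The allowance to perform an ECHO up to 3 weeks before the visit is ignored.

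**Step 4: does another provision catch the case?** The medical-monitor risk/benefit discussion in item 4 considers previous findings, but it is required only when the ECHO cannot be obtained within the stated allowance. A delay inside the 3 months does not trigger it. The PASP condition catches disease of these valves with raised pressure, but not regurgitation with PASP below 30 mmHg. The sponsor's rationale for the current Table 12 (Summary of Protocol Amendment 5.0, item 8) itself foresees moderate pulmonary and tricuspid regurgitation without indicators of pulmonary hypertension.

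**The case against.** The strongest reply is that a Level 2 or 3 subject does not simply carry on. Under Section 8.9.1 the drug is stopped unless the investigator and the parent both support continuing and a new consent is signed; Level 3 also requires more than 75% seizure improvement. The IPCAB Co-Chairs then prepare "an evaluation of the cardiopulmonary risk and proposed monitoring plan if applicable, for submission to the IDSMC", and the IDSMC decides. Its listed outcomes are to stop the drug, monitor more often, add measures or lower the dose. This stands, and it narrows the point to subjects whom the IDSMC keeps on drug. It does not remove it, because adding measures or lowering the dose can leave the ECHO interval unchanged.

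Second, the allowance runs from the protocol-designated due date, and an ECHO date ordered by the IDSMC is arguably not one. On that reading an IDSMC plan is exempt and there is no excess. The reading is reasonable, but Appendix 11 does not mention the IDSMC and does not say which instruction governs.

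Third, the delay rule is a separate screen, stricter than Table 12 for the aortic and mitral valves, and its criteria resemble the cardiac entry screen for de novo subjects (Section 4.1, criterion 10h). Part of the contrast is thus extra caution about Level 1 findings. That explains the 6-week limit for those findings, but not why a graded Level 2 or 3 finding is left out.

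A reader might infer that such subjects will go 180 days without an ECHO, or that valve disease has been missed. The documents support neither. The delay is permissive and limited to subjects unable to travel, the IDSMC reviews valve disease case by case (Section 4.4), and Section 1.3 reports that all abnormal-ECHO TEAEs among 330 subjects to the October 2019 cut-off were trace mitral or trace aortic.

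**Conclusion.** The point holds as a minor correction. As worded, Appendix 11, item 4 makes a subject with moderate or severe tricuspid or pulmonary regurgitation, absent aortic and absent or trace mitral regurgitation, and PASP below 30 mmHg eligible for the 3-month delay, while lesser Level 1 findings are held to 6 weeks. The 48-day figure assumes that the IDSMC has kept the subject on drug, that the routine 90-day interval is unchanged, and that the COVID allowance applies. A sufficiently shorter IDSMC interval, or an exemption for IDSMC plans, removes the excess, so the reversal of the oversight ranking is conditional and not a general consequence of the rule. Few if any subjects are likely affected, the rule is a temporary contingency, and no endpoint or analysis changes. The case for acting rests on consistency in a cardiac-safety rule and on the low cost of the repair.

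**What to change.** In Appendix 11, item 4 (Doppler ECHO):

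1. Add to the 3-month class: *and no Table 12 Level 2 or 3 finding on any valve*.
2. Add to the 6-week class: *or any Table 12 Level 2 or 3 finding on any valve; an IDSMC-set monitoring plan applies if stricter*.

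On the routine interval, a Level 2 or 3 subject would then wait at most 90 + 42 = 132 days, the same as the Level 1 subject, and the precedence question is settled. The change uses grades the central reader already reports and levels the item already cites. Its cost is that an occasional subject may need an earlier ECHO during COVID restrictions; the Sponsor-approved alternative facility already in item 4 eases this.
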